Intervention arm: The individuals who are randomized to the intervention arm will each receive an initial call from a care coordinator in the 3 months following randomization, which we will refer to as the "screening" call. The care coordinator will explain care coordination services as they usually would and offer to administer a survey to see if the patient is eligible for care coordination. If the patient agrees, the care coordinator will administer a previously validated telephone survey on perceptions of care coordination (see Kern et al. J Gen Intern Med 2020;35:3517-24). The care coordinator will document the survey responses in customized data entry forms that we will develop in REDCap, a secure web-based data management platform. If the patient responds to the survey in a way that indicates a perceived problem with care coordination in the past 6 months (i.e., a "positive" response to greater than or equal to 1 of 8 questions, as defined previously), then we will consider this a "positive screening." The REDCap tool will notify care coordinators at the end of the survey if the survey indicates a "positive screening." For patients and proxies whose screening calls were "negative" (not revealing a perceived problem with care coordination), the care coordinators will give them their contact information and invite them to reach out with any questions or concerns. For patients and proxies whose screening calls were "positive," care coordination will start narrowly, with the care coordinator seeking to understand the survey responses (exactly what the patient or proxy thinks is not working well and why). The care coordinator will then seek to address the issue, documenting the process in the EHR. The care coordinators will be free to engage in broader care coordination activities (e.g., general medication reconciliation, reviewing upcoming appointments, arranging transportation, etc.) at their discretion. The length and frequency of interactions between the care coordinator and patient or proxy will vary with the patient's needs and care coordinator's discretion. Patients will be followed for a minimum of 30 days and a maximum of 1 year.

Expected duration:

Participation will last up to 16 months after randomization. The events of the study are depicted below (Figure 2) and described in text that follows.

Figure 2. Timeline of events for each participant (not to scale)

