Secondary outcomes will consist of four implementation outcomes. Acceptability will be operationalized as the change in self-reported problems with care coordination at baseline vs. 1 month after the start of care coordination services. Appropriateness will be operationalized as: a) the types of problems with care coordination uncovered in response to the survey in the intervention group, and b) the frequency of different types of care coordinator activities in each group (i.e., facilitating provider-provider communication, facilitating transportation, etc.). Fidelity will be measured by tracking how many people in the intervention group are surveyed, how many report problems with care coordination, and how many of those receive care coordination services. Implementation Cost (or Efficiency) will be measured as the total number of care coordinator hours needed in each group. Acceptability will be measured with surveys, and the pre-post comparison will be made with McNemar's test to account for the paired nature of the data. The other implementation outcomes will be measured through manual review of the electronic health record, using a standardized abstraction tool, and reported with descriptive statistics.

Sample size and power:

This trial will include Medicare beneficiaries ≥ 65 years old who are: 1) attributed to NewYork Quality Care by the Centers for Medicare & Medicaid Services; 2) community-dwelling; 3) who have cardiovascular disease (CVD) or ≥ 1 CVD risk factor (defined as one or more of acute myocardial infarction, atrial fibrillation, diabetes, heart failure, hyperlipidemia, hypertension, ischemic heart disease, and stroke or transient ischemic attack), and 4) had highly fragmented ambulatory care in the past year (as a risk factor for gaps in communication among providers). We expect that approximately 6,000 individuals will meet these inclusion criteria.

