To determine how many of those 6,000 individuals we would include in the trial, we first calculated the sample size needed to determine a difference in the percentage of people in the intervention group who report a gap in care coordination at baseline vs. 1 month after receipt of care coordination services (Aim 2a). Based on our preliminary data, we assumed that 38% of people would report a gap in care coordination at baseline. Table 1 shows the sample size needed in the intervention group to find a range of effect sizes, using McNemar's test and assuming $\alpha = 0.05$, power = 80%, and correlation for paired observations of 50%. We then calculated the sample size needed to determine a significant difference in the percentage of people who experience an ED visit or hospitalization, comparing the intervention and control groups over the 12-month follow-up period (Aim 1). Using preliminary data from [name] R01 study sample, we found that 40% of Medicare beneficiaries with CVD or ≥ 1 CVD risk factor and highly fragmented ambulatory care in one year had an ED visit or hospitalization the following year. Table 2 shows the sample size needed in each group to find a range of effect sizes for that outcome, using a chi-square test, $\alpha = 0.05$, and power = 80%. Based on Tables 1 and 2, we will plan to include 400 people in the trial (200 per group), which will enable us to find statistically significant and clinically meaningful differences for both Aims.

Table 1. Sample size needed in the intervention group for change in self-reported gaps in care coordination pre- vs. post intervention

Effect size	Sample size
38% \pm 10%	178
38% \pm 12.5%	113
38% \pm 15%	79

Table 2. Sample size needed to detect difference in primary outcome between groups

Effect size	Sample size
40% \pm 15%	346 (173 per group)
40% \pm 20%	194 (97 per group)
40% \pm 25%	124 (62 per group)

The analysis will use all randomized participants with an intention-to-treat approach. The base case analysis will use complete data, and a sensitivity analysis will use multiple imputation for missing covariates.

H. DIRECT ACCESS TO SOURCE DATA

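### Acceptability is scored as any problem versus none, so partial improvement and worsening within positive patients go unregistered; a paired count of the eight items could be added cheaply

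*Combined protocol and SAP*

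**What the plan says.** Section C (Design, Intervention arm) has the coordinator administer an eight-question survey and enter the responses in REDCap. A patient screens positive on a "response to greater than or equal to 1 of 8 questions, as defined previously". For positive patients, coordination starts narrowly, "with the care coordinator seeking to understand the survey responses (exactly what the patient or proxy thinks is not working well and why".

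Section G (Analysis plan) defines Acceptability as the "change in self-reported problems with care coordination at baseline vs. 1 month after the start of care coordination services". That sentence names no scale. The test does: "the pre-post comparison will be made with McNemar's test to account for the paired nature of the data". McNemar's test takes a paired yes/no outcome.

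Section G (Sample size and power) confirms the scale. It sizes this outcome for a "difference in the percentage of people in the intervention group who report a gap in care coordination at baseline vs. 1 month", and "we assumed that 38% of people would report a gap in care coordination at baseline". The settings are alpha 0.05, "power = 80%, and correlation for paired observations of 50" percent. Table 1 gives 178, 113 and 79 patients for changes of 10, 12.5 and 15 points. The plan then says "we will plan to include 400 people in the trial (200 per group").

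Item-level responses are used only under Appropriateness, to list the types of problem uncovered. No before-and-after count is planned.

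**The concern.** The intervention works on individual problems, but the endpoint moves only when a patient crosses between zero and at least one. A positive patient registers as improved only if all eight items are negative at 1 month. Falling from four problems to one gives a pair that is positive both times and adds nothing to McNemar's statistic. So does rising from one to five, which means worsening among the patients who received coordination cannot be seen. One new, unrelated problem also cancels a resolved one. All of this follows from the scoring alone.

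Acceptability is meant to inform dissemination. A null any-versus-none result could be read as no improvement when patients in fact had fewer problems, and a count analysis added after the results are known would be post hoc.

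**Working it through.** **1. Reproduce Table 1.** Inputs from section G: p1 = 0.38, p2 = p1 − d, paired correlation 0.5, power 80%. Sidedness is not stated; two-sided 0.05 is used.

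- Both positive: p11 = p1·p2 + 0.5·√(p1·q1·p2·q2), where q = 1 − p.
- Discordant total: pd = p1 + p2 − 2·p11.
- n = [1.96·√pd + 0.8416·√(pd − d²)]² / d².

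For d = 0.10: p11 = 0.1064 + 0.1090 = 0.2154, pd = 0.2293, and n = (0.9385 + 0.3941)² / 0.01 ≈ 177.6. The other rows give 113.0 and 78.2. Table 1 says 178, 113 and 79, so it is a two-sided McNemar calculation on a binary outcome, for a fall from 38%. One-sided values (140, 89, 61) do not match. This confirms any-versus-none scoring.

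**2. What the scoring misses.** Suppose a patient has k problems, each resolving independently with probability r, and none new. Expected resolved problems are k·r. Those registered are k·r^k, because all k must clear. The unregistered share is 1 − r^(k−1). At r = 0.5 it is 0 for k = 1, 50% for k = 2 and 87.5% for k = 4.

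The documents give no distribution of k, so a range is needed. Assume beta-binomial counts with 38% positive, r from 0.3 to 0.7, and each absent item newly appearing with probability 0 to 0.02. The last column compares the pairs needed for 80% power at r = 0.5 with no new problems.

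| Mean problems per positive patient | Share of resolved problems unregistered | Pairs needed, McNemar vs paired count |
|---|---|---|
| 1.2 | 13–28% | 44 vs 33 |
| 1.6 | 28–52% | 52 vs 32 |
| 2.3 | 47–74% | 65 vs 31 |
| 3.5 | 68–89% | 97 vs 28 |
| 4.6 | 78–94% | 136 vs 24 |

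**3. Power with 200 pairs.** Assumed model: each patient has a personal probability of flagging an item, drawn from a beta distribution (concentration 4) set so that 38% flag at least one of eight. This gives a paired yes/no correlation of about 0.5, as in the plan, and about 2.05 problems per positive patient. Coordination lowers the item probability in screen-positives, and all 200 are surveyed again. The count is tested with the Wilcoxon signed-rank test.

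| Per-item reduction | Fall in percentage positive | McNemar | Count |
|---|---|---|---|
| 30% | about 4 points | 17% | 63% |
| 50% | about 7.5 points | 49% | 96% |
| 70% | about 13 points | 86–90% | 99% |

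With about 1.4 problems per positive patient (correlation about 0.22), the first two rows become 16% vs 24% and 34% vs 53%. With no effect, both tests reject in about 3–7% of trials. Simulation error is a few points.

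**4. Who is surveyed again.** Section G times follow-up from the start of services, and only screen-positives start services. Yet 38% of 200 is 76 patients, fewer than Table 1's 178 or 113, so the 10- and 12.5-point rows presuppose that screen-negatives are surveyed again. It matters. With no effect and correlation 0.5, p11 = 0.38² + 0.5 × 0.38 × 0.62 = 0.2622, so 0.38 − 0.2622 = 0.1178 of patients turn negative by chance, or 0.1178 × 200 ≈ 23.6. With everyone surveyed, as many turn positive and the two cancel. With positives only, nothing offsets them and McNemar's z is about √23.6 ≈ 4.9. The count test in positives only rejects in about 72% of no-effect trials under the concentration-4 model.

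**The case against.** The strongest reply is that the plan is coherent on its own terms. The any-problem rule comes with a survey described as previously validated, the 38% planning rate is on that scale, and Table 1 is right for it. With complete pairs, 200 exceeds 178. The 30% and 50% reductions correspond to falls below Table 1's smallest effect of 10 points; at about 13 points, within its range, McNemar already has about 86–90% power. The documents do not show that the eight items form an additive score, so making the count the main test would swap an established definition for an undocumented one. All of this stands. It argues for adding the count rather than replacing McNemar.

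A reader might infer that most of the measurable improvement is lost. The documents do not support that. If most positive patients report one problem, most improvement is registered. In the concentration-4 model about 48% of positives have exactly one problem and only about 14% have four or more, so the four-to-one example describes a minority.

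The reply does not remove the mismatch between an outcome described as change in problems and a score that sees only complete clearance.

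**Conclusion.** The point holds as a low-cost improvement. Acceptability is scored any-versus-none, so partial improvement, and worsening among patients already positive, is not registered. That needs no assumption. The size does: the unregistered share runs from about 13% to 94% over the distributions tried, and the documents do not narrow it. The count test was more powerful in every setting with an effect, by a wide margin at about two problems per positive patient and a modest one at about 1.4. These power figures rest on the assumed item model, 200 complete pairs, and a 1-month survey that repeats the same eight items.

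Table 1 is not in error. The outcome is one of four secondary implementation outcomes in a pilot trial, and the primary comparison of ED visits or hospital admissions is unaffected.

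**What to change.** In section G (Analysis plan), keep McNemar's test on any-versus-none, matching Table 1, and leave the screening rule in section C as it is. Add a pre-specified paired analysis of the change in the number of positive items (0–8), by Wilcoxon signed-rank test or as a mean change with confidence interval. State three things with it:

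- The 1-month survey repeats the same eight items.
- Both analyses include all intervention-arm patients surveyed at baseline, screen-negatives included. If only screen-positives are surveyed again, both results are reported as descriptive only, because regression to the mean alone would produce apparent improvement.
- The proportion of baseline-positive items that later become negative is not reported, or carries that same caveat, since it selects on a positive baseline.

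The cost is a few sentences and a small extra analysis of responses recorded in REDCap. Surveying screen-negatives at 1 month adds calls only if the plan did not already intend them. The downside is that the count is not the scale of Table 1 and its additivity is undocumented, so it should sit beside McNemar's test rather than replace it.

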This trial will be conducted in compliance with the protocol, good clinical practice, and applicable regulations.

C. TRIAL DESIGN

Primary endpoint:

The combined outcome of emergency department visit or hospital admission over 12 months of follow-up

Secondary endpoints:

[figure not shown]
(a) Acceptability (change in self-reported problems with care coordination after the intervention vs. before). (b) Appropriateness (frequency of different care coordination activities done). (c) Fidelity (percent of eligible individuals who receive care coordination services). (d) Efficiency (total number of care coordinator hours spent)

Design:

We will conduct a randomized controlled trial with a parallel design (Figure 1).

There are three main clinical entities within the ACO: Weill Cornell, Columbia, and NewYork-Presbyterian Hospital. These three entities have pre-existing care management teams, and the three entities serve different populations, based on geography within New York City and based on insurance type (such as dual eligible status). In order to remove any effect of clinical entity on the study outcome, we will conduct randomization stratified by clinical entity. We will take a random sample of people from each of the three clinical entities, such that each clinical entity will contribute one-third of the total sample.

The two study groups and the nature of the intervention are described below.

Usual care arm: The individuals who are randomized to usual care will receive care coordination services if they are identified by the ACO as eligible for them in the 3 months following randomization. Usual care consists of assigning attributed patients to care coordinators in response to: 1) a discharge from an NYQC hospital (approximately 80% of cases), 2) a discharge from a non-NYQC hospital (approximately 15% of cases), or 3) a referral from an NYQC physician asking for care coordination for a specific patient (approximately 5% of cases). An administrator at NYQC is responsible for querying daily the Epic electronic health record (EHR) to identify discharges from NYQC hospitals and for querying daily a New York City health

[figure not shown]

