*As above, we will consider the first 3 months after randomization to be the period in which participants can have a "qualifying event." For the intervention group, the qualifying event is a survey that indicates perceived problems with care coordination. For the usual care group, the qualifying event will typically be a hospital discharge or, rarely, a physician referral. Participants who have a qualifying event will then receive attention from care coordinators, with care coordination lasting for 1 month following the qualifying event (equivalent to 2-4 months after randomization, with optional continuation of care coordination at the care coordinator's discretion). Follow-up for the combined outcome of emergency department visit or hospitalization will continue for 12 months, beginning 1 month after the start of care coordination (equivalent to starting 3-5 months after randomization and ending 15-17 months after randomization).

Discontinuation:

Participants may discontinue care coordination at any time.

Measures to minimize bias:

We will use randomization to minimize bias. Masking will not be feasible for this trial, because the care coordinators will know if a patient has been discharged from the hospital or has received a survey to assess experiences with healthcare. This seems acceptable given that it is a pragmatic clinical trial, designed to determine comparative effectiveness in the real world.

Potential risks:

The risks involved in this study are minimal, as the receipt of care coordination (which seeks to facilitate communication among people involved in a patient's care) is part of standard clinical practice. The only study activity that is different from usual care is the administration of a telephone survey, which takes 7 minutes to complete. This survey has previously been successfully administered to more than 7,000 adults 65 years and older nationwide, with no adverse consequences reported by the team of people who conducted the data collection for that administration. It is theoretically possible that answering the survey could increase a respondent's anxiety about the complexities of navigating healthcare, although we expect any such increase to be mild and short-lived, because we will be providing immediate resources to

address the reported problems. The other risk is a breach of confidentiality, but we can take ample measures to minimize the likelihood that this occurs, as described below.

Steps taken to minimize risk:

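### The 12-month primary-outcome window starts from an arm-specific event after randomisation that most of the intention-to-treat sample will not have, and its stated end conflicts with the 16-month limit

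*Combined protocol and SAP*

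**What the plan says.** The primary endpoint in section C is "The combined outcome of emergency department visit or hospital admission over 12 months of follow-up", with no statement of when the 12 months begin. Section G (Analysis plan) names logistic, count and Cox regressions and gives no time zero for them.

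The only readable text that sets the start is the note to Figure 2 under Expected duration in section C. Follow-up "will continue for 12 months, beginning 1 month after the start of care coordination", which is glossed as "equivalent to starting 3-5 months after randomization and ending 15-17 months after randomization". Coordination goes to participants who have a qualifying event in the first 3 months, "with care coordination lasting for 1 month following the qualifying event" ("equivalent to 2-4 months after randomization"). In the intervention arm that event is a survey showing a perceived problem. The note continues: "For the usual care group, the qualifying event will typically be a hospital discharge or, rarely, a physician referral". The description of the usual care arm gives the mix of triggers as "a discharge from an NYQC hospital (approximately 80% of cases), 2) a discharge from a non-NYQC hospital (approximately 15% of cases", with physician referral making up the other 5% or so.

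Just before Figure 2 the plan says "Participation will last up to 16 months after randomization". Section G states twice that the analysis is by intention to treat, the second time specifying that all randomised participants are used.

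**The concern.** Time zero for the primary outcome is a date after randomisation, and what sets it differs between the arms. In usual care it is a discharge in about 95% of cases (80% + 15%), so the clock is usually started by an admission, which is itself an outcome-type event and falls outside the window it opens. In the intervention arm the clock is started by a telephone survey.

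Most people in either arm will have no such event. Taken literally, the rule gives them no window, yet they must be analysed. The analyst then has to supply an origin for most of the sample, and the possible choices do not all give the same answer. What is at stake is the definition of the primary endpoint, and with it the time scale of the Cox analysis and the counting period of the count analysis.

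**Working it through.** **1. The stated months.** Reading 2–4 as the months in which coordination starts reproduces the plan's figures: 2 + 1 = 3 and 4 + 1 = 5; adding 12 gives 15–17. Other readings do not:
- events at 0–3 months, plus 1, give a start at 1–4; plus 12, an end at 13–16;
- 2–4 read as the end of the coordination month (events at 1–3) gives a start at 2–4 and an end at 14–16.

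The latest end on these two readings, 3 + 1 + 12 = 16, matches the stated limit on participation. The plan's own upper figure, 17, exceeds it.

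**2. How many have no start date.** Inputs from section G (Sample size and power): 200 per arm, 38% reporting a gap at baseline, 40% with an ED visit or hospitalisation in the following year. Assumptions: all 200 intervention participants are surveyed; a share *s* of events are admissions (0.4–0.6, with 1.0 as the extreme); events occur at a constant rate, either the same for everyone (*v* = 0) or varying between people with gamma frailty variance *v* up to 2. As a further range, 50% screen positive.

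The event-free probability to month *t* is S(t) = exp(−mt) with m = −ln(0.6)/12 = 0.0426 for *v* = 0, and S(t) = (1 + vmt)^(−1/v) with m = (0.6^(−v) − 1)/(12v) for *v* > 0. For *v* = 2, m = 0.0741. Both give S(12) = 0.60. The usual-care share with an admission in 3 months is q = 1 − S(3s). The number undated is 400 − 200p − 200q, where p is the share screening positive.

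| *v* | *s* | q | undated, p = 0.38 | undated, p = 0.50 |
|---|---|---|---|---|
| 0 | 0.4 | 5.0% | 314 | 290 |
| 0 | 0.6 | 7.4% | 309 | 285 |
| 0 | 1.0 | 12.0% | 300 | 276 |
| 2 | 0.4 | 7.9% | 308 | 284 |
| 2 | 0.6 | 11.1% | 302 | 278 |
| 2 | 1.0 | 16.8% | 290 | 266 |

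Results for *v* = 1 lie between. Referrals (5% of cases) lower the count by at most 2. The range is therefore roughly 265–315 of 400.

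**3. Does the choice of origin matter when there is no true effect?**
- *Non-qualifiers at a fixed month 3 or 4, qualifiers 1 month after their event.* Given a person's own rate, every window is 12 months long and starts after whatever determined it. The risk is 40% in both arms and the bias is zero. Simulation gives −0.2 to +0.2 points, and −0.4 to +0.2 when risk is doubled for 1 or 3 months, or tripled for 1 month, after discharge.
- *Non-qualifiers at randomisation, qualifiers later.* Usual-care non-qualifiers are by selection free of admission for the first 3 months of their window. The spurious excess against the intervention is 0.60 − S(12 + 3s). For *v* = 0 and *s* = 0.4 it is 0.60 − 0.60 × exp(−1.2 × 0.0426) = 3.0 points; for *s* = 0.6, 4.4; for *s* = 1.0, 7.2. For *v* = 2 the three values are 1.8, 2.7 and 4.3. With 200 per arm the two-sided false-positive rate is about 7–15% for *s* = 0.4–0.6, and 14–33% for *s* = 1.0.

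**The case against.** **Figure 2 may hold the rule.** The text in question is a note to a per-participant timeline that is not reproduced, and it does express the window in months after randomisation. This stands: one can say only that the readable text lacks a start date for non-qualifiers. If the figure supplies one, it needs repeating in section G.

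**A reader might infer that the primary comparison is biased, or that power collapses.** The documents do not support either. On the reading nearest the written calendar, a fixed month 3 or 4 for non-qualifiers, the bias is essentially nil. The 2–7 point difference needs a mixed rule that the documents nowhere state. Analysing only the dated participants would cut power for 40% versus 25% from 90% to about 15–34%, but that means dropping people whom section G requires to be analysed.

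**A reader might infer that none of the month figures can be reconciled.** That goes too far. The 2–4, 3–5 and 15–17 figures agree if coordination starts in months 2–4; the 3-month limit applies to the qualifying event, and outreach can follow it. If the figures are ordinal months, the start of the 17th month is 16 elapsed months and even the last conflict closes. The text states neither convention, so 17 against 16 still needs a clarifying sentence.

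**The count is derived, not quoted.** This is correct. The 38% comes from adults aged 65 and over in general, not a highly fragmented population, and the admission share is assumed. Treating the 20–30% who decline coordination as undated would raise the count to about 319–347, but the note ties coordination to the qualifying event, so decliners are not counted here. More than half the sample is undated throughout these ranges.

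**Monthly claims review.** Section F has the research team analyse claims for these outcomes each month. That is safety tracking, and no interim analyses are planned. It is a reason to fix the window early, not evidence that it would be chosen after seeing data.

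**Conclusion.** The concern holds as a defect in the definition of the primary endpoint. The stated start depends on an event after randomisation that differs by arm. It leaves roughly 265–315 of 400 participants without a start date in the readable text, and it cannot be combined with an analysis of everyone randomised. The end of follow-up (15–17 months) also disagrees with the 16-month limit on participation, unless a labelling convention that the plan does not state is assumed.

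The count rests on the plan's 38% and 40% rates (or 50% screening positive), full survey completion, an assumed admission share of 0.4 to 1.0, and constant individual event rates. No bias is demonstrated on the most natural completion of the rule. The harm is an open choice in the primary endpoint, where one conceivable completion would produce a false difference of about 2–4 points, or up to about 7 if every event were an admission.

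**What to change.** In section G, define one 12-month window at a fixed time from randomisation, the same for every participant in both arms and independent of any qualifying event. Use it for the logistic, count and Cox analyses. Name it as primary before outcome data are analysed, and report the alternative as a sensitivity analysis. Two choices are defensible:
- **Months 4–16**, which fits 3 + 1 + 12 = 16.
- **Months 0–12**, which fits the basis of the 40% rate, a rate for the year following the fragmentation year.

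Reconcile the 15–17 and 16-month figures, stating whether months are elapsed or ordinal.

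The cost is protocol and SAP wording; the same claims data serve. The choice of window is a real trade-off. With a constant rate, 12% of participants have a first event by month 3 and 16% by month 4 (17% and 21% with frailty variance 2), and a month 4–16 window leaves these early events uncounted. For a hazard effect equivalent to 40% versus 25%, beginning at a call spread evenly over months 0–3, power with 200 per arm is:

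| Effect lasts | Months 4–16 | Months 0–12 |
|---|---|---|
| throughout | 90% | 79% |
| 12 months after the call | 69% | 79% |
| 6 months after the call | 13% | 31% |

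Neither window is better in every case, so the team should choose according to how long it expects the effect to last.

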This trial will use data from three sources: survey responses, Medicare claims (for the inclusion criterion of fragmentation and for the outcome of emergency department visit or hospital admission), and EHR chart review (for baseline demographics and for secondary outcomes).

Analysis plan:

We will track patient participation in both study groups. We will compare the characteristics of the patients in each study group, using chi-squared tests for dichotomous variables and t-tests for continuous variables, to confirm that the study groups are balanced ($p > 0.05$). We will calculate the percentage of participants in each study group with an ED visit or hospitalization (primary outcome), the numbers of ED visits and hospital admissions in each study group (sensitivity analysis), and the time-to-event in both groups (sensitivity analysis). We will use logistic regression to compare study groups for the combined outcome of any ED visit or hospital admission, adjusting for any co-variates that were imbalanced between the study groups at baseline. We will do the same with Poisson regression (or zero-inflated Poisson regression as appropriate based on the distribution of counts) for number of ED visits or hospital admissions and Cox regression to compare study groups for the time to first ED visit or hospitalization. We will conduct analyses using an intention-to-treat approach, considering all individuals as members of the group to which they were randomized. We will conduct exploratory moderator analysis with race and sex as potential moderators of treatment effect by introducing moderator x treatment interactions to our regression models.

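### The count sensitivity analysis names only Poisson or zero-inflated Poisson regression and makes no provision for overdispersion, so with default standard errors its p-values and intervals are likely to be too optimistic

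*Combined protocol and SAP*

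**What the plan says.** Section G, Analysis plan, sets out three comparisons of the groups.

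- Primary: "We will use logistic regression to compare study groups for the combined outcome of any ED visit or hospital admission".
- Sensitivity, counts: the plan reports "the numbers of ED visits and hospital admissions in each study group (sensitivity analysis") and models them with "Poisson regression (or zero-inflated Poisson regression as appropriate based on the distribution of counts) for number of ED visits or hospital admissions".
- Sensitivity, time to first event: Cox regression.

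Covariates enter only if they are imbalanced at baseline. The only departure from Poisson that the plan foresees is a switch to the zero-inflated form. The document mentions no overdispersion check, negative binomial or quasi-Poisson model, or robust standard error, and it does not say how standard errors will be obtained.

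**The concern.** A Poisson model sets the variance of the count equal to its mean. That holds only if patients with the same covariates share one underlying event rate. The eligibility criteria make this unlikely: a patient may qualify on hyperlipidemia alone, or with heart failure, stroke or a myocardial infarction. The three clinical entities also serve different populations. Because covariates are added only for imbalance, the model may contain little beyond treatment, and differences in rate between patients then appear as extra variance.

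Zero-inflated Poisson deals with part of this. It adds a group of structural zeros, which raises the variance/mean ratio to 1 + (inflation probability × Poisson rate). Among the remaining patients it still assumes Poisson spread.

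If the standard error is too small, the analysis meant to test the robustness of the primary result could show a nominally significant difference where there is none. The exploratory race and sex interactions would share the problem if they are also fitted in the count model.

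**Working it through.** **Inputs from the document.** Section G, Sample size and power: "we found that 40% of Medicare beneficiaries with CVD" or at least one risk factor, and with highly fragmented care, "had an ED visit or hospitalization the following year". So P(0 events) = 0.60. Size: "we will plan to include 400 people in the trial (200 per group"). Section C gives the window: "Follow-up for the combined outcome of emergency department visit or hospitalization will continue for 12 months".

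**The plan's own figure.** The document gives no mean, variance, dispersion or power for the counts. The nearest stated figure is Table 2, for the binary outcome. A two-sided 5% chi-square test with 80% power, pooled variance and no continuity correction, for 40% vs 55%, 60% and 65%, gives 173, 97 and 62 per group. These match Table 2, so 40% is a sound anchor.

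**Step 1: the Poisson case.** P(0) = exp(−m) = 0.60 gives m = −ln 0.60 = 0.51. With any overdispersion of negative binomial form and P(0) held at 0.60, the mean must be above 0.51.

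**Step 2: overdispersion consistent with 40%.** Take negative binomial counts with variance m + a·m², so that P(0) = (1 + a·m)^(−1/a). Set this to 0.60 and solve for a at assumed means m. The variance/mean ratio is V/m = 1 + a·m.

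- m = 0.6: a = 0.614, V/m = 1 + 0.614 × 0.6 = 1.37
- m = 0.8: a = 1.642, V/m = 1 + 1.642 × 0.8 = 2.31
- m = 1.0: a = 2.390, V/m = 1 + 2.390 × 1.0 = 3.39

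**Step 3: effect on the test.** With n per group and no treatment effect, the Poisson variance of the log rate ratio is 2/(n·m), while the true variance is (2/(n·m)) × (V/m). The true standard error is therefore √(V/m) times the reported one. At m = 0.8 and n = 200, the reported value is √(2/160) = 0.112 and the true value is 0.112 × 1.52 = 0.170. The true two-sided type I error is 2 × [1 − Φ(1.96/√(V/m))].

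| Assumed mean | V/m | √(V/m) | Poisson, formula | Poisson, simulated | Zero-inflated Poisson, simulated |
|---|---|---|---|---|---|
| 0.51 (true Poisson) | 1.00 | 1.00 | 5.0% | 6.0% | 4.1–5.7% |
| 0.6 | 1.37 | 1.17 | 9.4% | 9.3% | about 6% |
| 0.8 | 2.31 | 1.52 | 19.8% | 19.5% | 14–16% |
| 1.0 | 3.39 | 1.84 | 28.7% | 28.6% | 19–21% |

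The simulations use 200 per group and no treatment effect. The Poisson figures in the last three rows come from 40,000 trials. The first row comes from 1,500 trials (Monte Carlo standard error about 0.6 points), so its 6.0% is not a material departure from 5%. The zero-inflated figures come from several smaller runs, the smallest with 400 trials (standard error nearly 2 points), and are given as ranges for that reason.

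**Step 4: the remedies.** At the three assumed means, type I error was 5.0%, 5.4% and 5.2% for negative binomial regression, and 5.1%, 5.7% and 5.6% for Poisson with sandwich errors (2,000 trials each).

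**The case against.** The strongest reply is that the plan does not prescribe a wrong standard error. It is silent, and an analyst could fit the named Poisson model with sandwich errors without departing from the text. This is true: a reader might infer that default model-based errors are specified, and they are not. But a model named without qualification is ordinarily fitted with software defaults, so the silence does not protect the analysis.

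Second, the inflation rests on a dispersion that the document does not give. This stands. The result is conditional on the assumed means, and with truly Poisson counts the problem vanishes.

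Third, zero-inflated Poisson absorbs part of the extra variance and is close to nominal in the mildest case (about 6% at a mean of 0.6). This also stands, so it would be wrong to say that the fallback always fails. It does not hold at means of 0.8 and 1.0.

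Fourth, this is a labelled sensitivity analysis in a pilot trial. The logistic and Cox analyses use one outcome per patient, and the sample size rests on the binary outcome. None of these is touched.

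Three further readings are tempting but unsupported. One is that repeat use by a patient is ignored: it is already in that patient's total, and what is missed is extra variation between patients. Another is that an ED visit ending in admission will be counted twice: the plan does not say whether the two counts are summed or analysed separately. The third is that a follow-up offset is needed: planned follow-up is a fixed 12 months, and nothing examined here shows a need for one.

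**Conclusion.** The point holds as a conditional one. The plan names two count models, neither of which allows for overdispersion among users of care, and provides no correction. With default errors, inference is likely to be too optimistic in this population: type I error of about 9%, 20% and 29% for Poisson and about 6%, 14–16% and 19–21% for zero-inflated Poisson, at assumed means of 0.6, 0.8 and 1.0. These figures assume negative binomial counts, 40% of patients with any event, 200 per group and treatment as the only covariate. They do not show that the p-values will certainly be wrong, since the dispersion is unknown. A reader might also infer that the trial's main conclusion is at risk. The document does not support that, because the primary analysis is logistic regression on a binary outcome.

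**What to change.** Replace the count-model sentence in section G, Analysis plan, with wording such as: *The number of ED visits or hospital admissions will be compared between study groups using negative binomial regression, or Poisson regression with robust (sandwich) standard errors.* This takes the place of Poisson or zero-inflated Poisson with default errors. It is best to pick one of the two options before the groups are compared; both held close to 5% in the checks above.

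The change is one sentence, with no effect on data collection or sample size. The downside is a wider confidence interval for the rate ratio in this sensitivity analysis. Relative to default Poisson errors, the interval on the log scale would be about 1.17, 1.52 or 1.84 times as wide at the three assumed means, and essentially unchanged if the counts are truly Poisson.
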